### 5.3 Derived variables

None of the variables related to the primary and secondary endpoints are calculated using additional variables from the data recorded in the CRF, with the exception of change scores that will be calculated as indicated in the previous 2 sections.

[figure not shown]
## 6 Study Methods

### 6.1 General Study design and Plan

This is a single-site, randomised, double-blind, placebo-controlled, parallel, phase IIb clinical trial. Participants will receive IV Scopolamine or placebo in addition to their current treatment regimen. At Visit 2, all participants will receive placebo run-in (100mls of Saline IV). Within 7 days of Visit 2, participants will be assessed against the placebo run-in criteria and if these criteria are met they will be randomised (visit 3) to receive either placebo or 4 µg/kg Scopolamine IV in 100mls of Saline over 15 minutes at Visit 3 (Day 0), Visit 4 (days 2-6) and Visit 5 (days 6-10).

A flow-chart and schedule of assessments are included for greater clarity.

SCOPE-BD NUIG-2017-002, Statistical Analysis Plan Version 1, 19/03/2024

Note timeline between visits:

Visit 1 and 2: ≤14 days. Can also occur on the same day and thus data from screening visit does not need to be replicated at Visit 2  
Visit 2 and 3: ≥2 days and ≤7 days  
Visit 3 and Visit 4 and Visit 5 and Visit 6: ≥2 days  
Visit 6 and Visit 7: ≥3 days

SCOPE-BD NUIG-2017-002, Statistical Analysis Plan Version 1, 19/03/2024

Procedures	Visit 1			Visit 2			Visit 3			Visit 4			Visit 5			Visit 6			Visit 6			Visit 7			
	Screening			PLACEBO IV Infusion			Randomisation Day 0 Scopolamine or Placebo IV Infusion			Day 4 ( $\pm$ 2 Days) Scopolamine or Placebo IV Infusion			Day 8 ( $\pm$ 2 Days) Scopolamine or Placebo IV Infusion			Day 15 ( $\pm$ 5 Days) Follow-Up			Day 29 ( $\pm$ 7 Days) Follow-Up						
	Pre	During	Post	Pre	During	Post	Pre	During	Post	Pre	During	Post	Pre	During	Post	Pre	During	Post	Pre	During	Post	Pre	During	Post	
Signed informed consent	X						X**																		
Inclusion/Exclusion	X	X					X																		
Demographics																									
IWRS							X																		
Demography	X																								
MEHI	X																								
Medical/Surgical History/History BPD	X																								
Current Medication	X			X			X																		
Vital Signs – HR, BP & RR	X	X	X	X	X	X	X	X	X	X	X	X	X	X	X	X	X	X	X	X	X	X	X		
SCID-RV	X																								
HDRS	X	X																							
YMRS	X	X					X																		
AUDIT	X																								
Pregnancy Discussion	X	X					X																		
Contraception Advice	X	X					X																		
Serum Pregnancy Test a	X																								
Pregnancy urine dipstick A	X	X					X																		
UML, LFTs, TFTs b	X	X																							
Personality	X																								
CGI-S	X						X																		
CGI-I																									
VAS	X		X				X																		
MADRS	X		X				X																		
GAF																									
ECG	X																								
Height/Weight/Bmi	X																								
IV Cannulation	X						X																		
Infusion administration																									
Adverse Events	X	X	X	X	X	X	X	X	X	X	X	X	X	X	X	X	X	X	X	X	X	X	X		
Cannulation Site Check	X		X		X		X		X		X		X		X		X		X		X		X		
POMS (Optional)	X		X		X		X		X		X		X		X		X		X		X		X		
CANTAB ** (Optional)	X						X																		
WAIS c (Optional)			X*				X*																		
NEO-PI-FFI c (Optional)	X*		X*				X*																		
PRISE c (Optional)	X*		X*				X*																		
Subsidiary Assessment							X																	X	

Randomisation will only occur at Visit 3 after HDRS is demonstrated to be  $\geq 8$  and YMRS  $< 6$ . These measures will be conducted pre-randomisation (and consequently also pre-infusion).

Pre-infusion vital signs should be taken post cannulation. Post-infusion vital signs within 15 minutes of infusion stopping and 50 to 90 minutes post-infusion.

Visit 6 and 7 can be conducted by telephone in limited circumstances if a participant has withdrawn or is unwilling/unable to attend clinic at the scheduled time.

\* Can be undertaken at any of the marked visit

\*\* These include Paired Associates Learning (PAL), Spatial recognition, Delayed Match to Sample, ID-ED Shift, motor screening and Eyes of the Mind tests.

\*\*\*Only inclusion criterion 7 and exclusion criteria 21 and 22 are required to be met for randomisation at Visit 3 only

A Pregnancy test (serum pregnancy test and pregnancy urine dipstick), when required, for female participants only. Serum result confirmed prior to Visit 3.

B Blood tests for U&Es (Urine and Electrolytes), LFTs (Liver Function Tests) and TFTs (Thyroid Function Tests) should be confirmed within acceptable ranges in the previous 4 months of the Screening (Visit 1). Can be performed if required at Visit 1 or 2 (results must be confirmed as acceptable prior to infusion).

AUDIT = Alcohol Use Disorder Identification Test; BP = Blood Pressure; CANTAB = Cambridge Neuropsychological Test Automated Battery, CGI-I = Clinical Global Impression – Improvement, CGI-S= Clinical Global Impression- Severity, ECG= Electrocardiograph; Fagerstrom: Test for Nicotine Dependence, GAF = Global Assessment of Functioning; HDRS = Hamilton Depression Rating Scale; HR = Heart Rate; IV = Intravenous; IWRS = Interactive Web Response System; MADRS = Montgomery and Asberg Depression Rating Scale; MEHI = Modified Edinburgh Handedness Inventory; NEO PI-FFI = NEO Personality Inventory-Five Factor Inventory; POMS = Profile of Mood States; PRISE= Patient Rated Inventory of Side Effects; RR = Respiratory Rate; SCID-RV = Structured Clinical Interview for DSM; VAS = Visual Analogue Scale; YMRS = Young Mania Rating Scale; WAIS = Wechsler Adult Intelligence Scale.

Note timeline between visits:

Visit 1 and 2:  $\leq 14$  days. Can also occur on the same day and thus data does from screening visit does not need to be replicated at Visit 2.

Visit 2 and 3:  $\geq 2$  days and  $\leq 7$  days

Visit 3 and Visit 4 and Visit 5 and Visit 6:  $\geq 2$  days

Visit 6 and Visit 7:  $\geq 3$  days

## 6.2 General Study Population

Participants will be (male and female) adults who have bipolar disorder (bipolar disorder 1 or 2) and are experiencing a depressive episode of at least moderate severity as measured by a HDRS of  $\geq 14$  at Visit 2.

Participants will be attending the Galway-Roscommon Mental Health Services, including a specialised bipolar clinic in Galway and referred due to experiencing a depressive episode by their treating clinical team; or patients who have previously attended University of Galway / HRB-CRFG with an interest to participate/or have participated in research and have indicated a willingness to engage in future research; or patients who approach the research group directly requesting participation.

Once participants have consented to the trial they will be reviewed against the inclusion and exclusion criteria at the screening visit (Visit 1).

## 6.3 Randomisation and Blinding

Participants will be randomly assigned to receive either scopolamine or placebo in a 1:1 ratio. Randomly permuted blocks of sizes 4 and 6 will be used to ensure similar numbers of participants in each arm of the trial.

Randomisation will be stratified by the HDRS score at trial entry (a score of  $<23$  indicating a mild-moderate depressive episode and a score  $\geq 23$  indicating a severe depressive episode) to ensure greater balance between arms in the final trial sample and increase the efficiency of our treatment effect estimates.

A validated randomisation system will be used at Visit 3, (after HDRS and YMRS are completed) to randomise patients to either arm. This centralised system will ensure allocation concealment; preventing blinded trial staff from knowing which treatment group will be allocated. Blocks of randomly varying length will also reduce the predictability of the allocation sequence.

This trial will be conducted in a double-blind fashion with placebo control identical to Scopolamine solution to avoid bias in the assessment of outcomes. Site Investigators, site personnel, participants, and outcome assessors will be blinded to treatment allocation.

## 7 Sample Size

The primary outcome in this study is the Hamilton Depression Rating Scale score (HDRS). It is judged that a decrease of 50% or more in the HDRS score between randomisation and Visit 6 will be sufficient to consider a patient to have experienced a response. We anticipate that the average HDRS score in the proposed population pre-randomisation will be 24 units and that this outcome variable will be approximately normal. Based on results from the literature, it is estimated that a range of plausible values for the standard deviation is between 5 to 13 units.

SCOPE-BD NUIG-2017-002, Statistical Analysis Plan Version 1, 19/03/2024

Using this information, a sample of 44 participants (22 in each group) will have 85% power to detect a difference of 12 units between the treatment and control arms, i.e. an expected HDRS mean score of 12 in the treatment group vs. an expected HDRS mean score of 24 in the control group after Visit 6. The sample size is based on a 2-sample t-test (two-sided) with a standard deviation of 13 units (conservative approach) and a significant level of 0.05. Allocating 25 participants to each arm will ensure power  $\geq 85\%$  when loss to follow-up is  $< 12\%$  (6 participants missing at Visit 6 follow up).

## 8 *Timing of analyses*

### 8.1 Interim analyses

There are no planned interim analyses for this study with the exception of the following: A Data Safety and Management Board (DSMB) will be established to perform on-going safety surveillance and to review interim analyses on the safety data. All analyses for the DSMB will be conducted by the independent statistician who is a member of the DSMB.

### 8.2 Final analyses

All final analyses identified in the protocol and in this SAP will be performed after the last patient has completed the study. If a participant withdraws before completing the study, the reason for withdrawal will be documented and reported.

Before carrying out the analyses, the data manager's team at CRFG is responsible for the database cleaning process to ensure the integrity of the analyses. The database will be locked prior to the initiation of the analysis.

Any post-hoc exploratory analyses completed to support planned study analyses, which were not identified in this SAP, will be documented and reported in appendices to the Clinical Study Report (CSR).

## 9 *Analysis populations*

**Screening Population:** all subjects who provide informed consent and provide demographic and/or baseline screening assessments, regardless of the subject's treatment status in the study.

**Intent-to-treat Population:** all patients who randomised to treatment.

Effectiveness and safety outcomes will be analysed on an intention-to-treat basis for all participants randomised and with available follow-up data as per their randomised allocation. Safety outcomes will be evaluated on all participants who received at least 1 dose of treatment after randomisation (**Safety set**).

A **per-protocol** dataset is not well-defined under multiple treatments, here it could reasonably be defined as those participants who either received at least 1, at least 2

SCOPE-BD NUIG-2017-002, Statistical Analysis Plan Version 1, 19/03/2024 or all 3 IV treatments after randomisation. Sensitivity analyses will thus be performed on the primary outcome to assess efficacy of the treatment compared to placebo by incorporating the original allocation of participants and their level of adherence to treatment. This will involve examining the short term-effect of treatment in a longitudinal model and the overall effect of number of IV treatments received at follow-up visits after the final IV treatment.

## **10 General issues for Statistical Analysis**

### **10.1 Software used for the analysis**

All the statistical analyses will be carried out in R statistical software (version 3.6.0 or higher) unless otherwise noted by the statisticians assigned to this study. Primary and secondary analysis will be reviewed by an independent statistician, and all the code generated will be kept by the study statistician.

### **10.2 Methods for Withdrawals, Missing Data, and Outliers**

Any missing data which occurs will be summarised and reasons given. As per the statistical analysis specification, an inverse probability weighting will be performed in the primary outcome analysis (weights based on the inverse probability of a patient's data being missing given their pre-randomisation measurements). This will ensure the estimate and inference is more representative of all patients randomised.

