Mode of administration	15 minutes IV infusion

Placebo	Saline (Sodium Chloride 0.9%)
Dose	100 ml
Mode of administration	15 minutes IV infusion
Duration of treatment	Run-in period will be a maximum 21 days. The treatment period will be a maximum 10 days and the maximum number of days for follow up is 28 days
Primary endpoint	The primary endpoint will be the change in severity of objective depressive symptoms as measured by change in HDRS score from pre-randomisation (pre-IV infusion at Visit 3) compared to Visit 6.
Secondary endpoints	These include change in severity of depressive symptoms at study Visits 3, 4, 5, 6 and 7 and changes in cognitive scores at Visit 6
Statistical methods	The primary analysis of the primary outcome will estimate the difference in change in HDRS score between groups from pre-randomisation (pre-IV on Visit 3) to Visit 6 (with treating scores as continuous variables). Secondary outcomes will be analysed as appropriate to the distribution of each outcome, comparing the difference between groups at the specified follow-up visits. Pre-randomisation variables predictive of each outcome; and stratifying variables will be included in ANCOVA or generalised linear models of outcome variables. Inverse probability weighting will be used to account for missing outcome data and loss to follow-up at a given follow-up visit.

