11.5 Effectiveness analysis

11.5.1 Primary effectiveness analysis

For the primary effectiveness analysis of the primary outcome, it is expected that pre-randomisation measurements of the HDRS score will be correlated with the scores obtained at Visit 6 of treatment. The mean scores at Visit 6 will be compared across the study arms using an ANCOVA model. The response variable will be the change in HDRS score from Visit 3 to HDRS at Visit 6 including the HDRS score at Visit 3 as a covariate in the model. The addition of stratifying variables and other variables as covariates will be considered as appropriate and specified in the statistical analysis plan. This analysis will increase the power to detect significant differences between the groups.

Inverse probability weighting will be applied to the primary outcome analysis. These weights will be derived based on the inverse of the probability of a patient's data being missing given their pre-randomisation measurements. This will ensure the estimate and inference is more representative of all patients randomised, reducing bias in the estimation of the treatment effect due to participants lost to follow-up and missing data.

Inference regarding the treatment effectiveness will focus on the point estimate, confidence interval and p-value for hypothesis confirmation.

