### **10.5 Multiple Testing**

The power of this trial is based on a single analysis that focus only on the primary endpoint. The remaining secondary analyses will be considered exploratory and hypothesis generation and therefore no methods will be used to preserve the overall significance level (as in multiple testing procedures).

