## 13.2 Secondary Efficacy Analyses

Secondary outcomes will be analysed as appropriate (according to the distribution of each outcome), comparing the difference between groups at the specified follow-up visit and relative to baseline value (where specified/measured). Baseline variables predictive of each outcome (the measure at baseline where available), and stratifying

SCOPE-BD NUIG-2017-002, Statistical Analysis Plan Version 1, 19/03/2024  
variables will be included in ANCOVA or generalised linear models of outcome variables.

For secondary outcomes, the focus will be on the point estimates and confidence intervals for hypothesis generation.

Additional analysis of the primary outcome will compare the time course of HDRS under placebo and treatment using a mixed-effects model including fixed-effects terms for time since randomisation/study visit, trial arm and their interactions, and a random effect to account for correlation of multiple observations per participant.

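### The synopsis and the SAP disagree on which outcomes receive missing-data weighting, and the single-visit secondary analyses leave already collected scores unused

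*SAP*

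**What the plan says.** **Scope of the weighting.** The Statistical methods entry of the protocol synopsis describes the primary analysis, then the secondary models, and ends: "Inverse probability weighting will be used to account for missing outcome data and loss to follow-up at a given follow-up visit". Nothing there limits it to the primary outcome. Protocol 11.5.1 is narrower: "Inverse probability weighting will be applied to the primary outcome analysis". Protocol 11.8 and SAP 10.2 and 13.1 say the same; SAP 10.2 has "an inverse probability weighting will be performed in the primary outcome analysis". Wherever the weights are described, they are built from pre-randomisation measurements only.

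**Secondary outcomes.** SAP 9 analyses effectiveness "for all participants randomised and with available follow-up data as per their randomised allocation". SAP 13.2 compares arms at the specified visit. Its covariates are introduced as "Baseline variables predictive of each outcome (the measure at baseline where available), and stratifying" factors, and these "variables will be included in ANCOVA or generalised linear models of outcome variables". No missing-data method is named. Protocol 11.5.2 had left the complete specification of these models to the SAP.

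**Longitudinal modelling.** Only HDRS gets it: "Additional analysis of the primary outcome will compare the time course of HDRS under placebo and treatment using a mixed-effects model".

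**Status.** SAP 10.5: "The remaining secondary analyses will be considered exploratory and hypothesis generation". Protocol 11.7 ties the 0.05 level to the primary analysis alone.

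**The concern.** There are two linked problems. First, a reader of the synopsis expects weighting for every outcome at every follow-up visit, while a reader of the protocol body or the SAP expects it for one outcome. Whoever writes the code must choose.

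Second, an ANCOVA or generalised linear model at Visit 7 uses the baseline and the Visit 7 score. Someone seen at Visits 4, 5 and 6 but not at Visit 7 contributes nothing, although the earlier scores show how that person was doing. If leaving depends on those scores, the participants who remain no longer represent those randomised. Protocol 8.11 lists grounds for stopping that track worsening illness (risk of self-harm, ECT, involuntary detention) and one that could differ by arm (post-infusion haemodynamic events needing treatment).

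At stake are the estimates and intervals on which SAP 13.2 says secondary interpretation will rest. The primary result is not affected.

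**Working it through.** **1. The passages side by side**

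| Place | Outcomes weighted |
|---|---|
| Protocol synopsis | Missing outcomes at a given follow-up visit, no limit stated |
| Protocol 11.5.1, 11.8 | Primary outcome |
| SAP 10.2, 13.1 | Primary outcome |
| SAP 13.2 (secondary) | None mentioned |

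The split already exists inside the protocol; the SAP follows the protocol body.

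**2. The plan's own loss figure.** SAP 7 allows 6 missing at Visit 6: 6/50 = 12%, leaving 44, or 22 per arm. With a 12-unit difference and SD 13, the noncentrality is 12 / (13 × √(2/22)) = 12/3.92 = 3.06 on 42 df. Two-sided power at 0.05 is 84.9%, against the stated 85%. Nothing proposed here changes that.

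**3. What a single-visit analysis leaves out** (protocol 8.3.5, 8.3.6, Table 2)

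| Scale | Baseline | Post-randomisation visits |
|---|---|---|
| MADRS | 3 | 4, 5, 6, 7 |
| CGI-S | 3 | 4, 5, 6, 7 |
| GAF | 3 | 5, 6, 7 |

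**4. Size at Visit 7.** The documents give no dropout mechanism and no loss figure for Visit 7, so these inputs are assumptions: 25 per arm, true effect 8 points, SD 9, correlation 0.8 between adjacent visits, and dropout before Visit 7 driven by the Visit 6 score. The planned 12% is carried over from Visit 6. Understatement = 1 − (complete-case estimate / full-data estimate).

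| Dropout rule, about 12% missing | Full data | Complete case | Understated |
|---|---|---|---|
| Same rule on the raw Visit 6 score | 7.95 | 7.58 | 0.37/7.95 = 5% |
| Same rule on the score relative to its arm mean | – | – | about 0% |
| Opposite rules by arm | 8.07 | 6.97 | 1.10/8.07 = 14% |

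A second run of the opposite rules gave about 15%. The result depends on how steeply dropout follows the score. Over log-odds slopes of 0.7 to 2 per SD, the same raw-score rule gave 3–10% and opposite rules 11–23%; a slope of 1 gave about 4% and 14%. An estimator using Visits 3–6 and arm came within 1% of the full-data effect.

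For scale, the Visit 3 to Visit 7 correlation is 0.8⁴ = 0.41, so with 22 per arm the ANCOVA standard error is about 9 × √(1 − 0.41²) × √(2/22) = 2.5 points. A 5% understatement is 0.4 points, and 15% is 1.2 points, or about half a standard error.

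**5. Would the baseline-only weights help?** A large-sample simulation (assumed true effect −6, SD 9, 10–13% missing) compared baseline-adjusted complete-case ANCOVA with and without weights based on baseline.

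| Missingness depends on | Bias, unweighted | Bias, weighted |
|---|---|---|
| Nothing | 0.00 | 0.00 |
| Baseline | −0.02 | −0.02 |
| Baseline, differently by arm | 0.01 | 0.01 |
| Post-baseline score | 0.15 | 0.15 |
| Post-baseline score, differently by arm | −0.86 | −0.86 |
| The unseen outcome | 0.28 | 0.28 |

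Where dropout follows baseline there is no material bias to remove. Where bias exists, these weights leave it unchanged. The −0.86 is an overstatement of 0.86/6 = 14%, because here the drug arm lost participants with poor scores and the placebo arm those with good scores. The direction is therefore not fixed.

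**The case against.** The strongest reply is that bias is not established, and that stands. A reader might infer from the SAP that the secondary results will be biased by dropout. The documents do not support this: they state no mechanism, the models adjust for baseline, and step 5 shows no material bias when dropout depends on baseline alone. Complete-case analysis is itself an inference from SAP 9 and 13.2, because weighting of secondary outcomes is not expressly excluded.

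A reader might also infer that carrying out the synopsis sentence in full would cure the problem. Step 5 shows that it would not. The scope conflict and the choice of model are separate matters.

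Larger figures can be produced. With 21–30% missing and opposite dropout by arm, the understatement reaches 25–41%. That loss is about twice the planned 12%, and the rule requires drug-arm participants who are doing well to leave. Side effects are a weak reason for this: infusions end at Visit 5, and protocol 17.4.1.4 describes effects lasting under 3 hours. The opposite-rule rows are best read as a stress test.

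The plan also limits loss. Visits 6 and 7 may be held by telephone, people who stop infusions are asked to continue assessments, and missing data will be summarised with reasons. HDRS at Visit 7 is already covered by the planned mixed model. These outcomes are exploratory.

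The textual conflict remains, as does the fact that the stated secondary method leaves collected scores unused when a method that uses them is already planned for HDRS.

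**Conclusion.** The point holds as an inconsistency to reconcile and an inexpensive improvement to exploratory analyses. The synopsis and the rest of the documents differ on the scope of weighting, and SAP 13.2 has no missing-data method for secondary outcomes. On its natural reading, MADRS, GAF and CGI-S contrasts at Visits 6 and 7 ignore earlier scores of anyone absent at that visit.

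The risk is conditional on dropout following post-baseline scores. At 12% loss, an 8-point effect at Visit 7 is understated by about 0–5% under similar rules in the two arms and by about 15% under opposite rules. Steeper dropout raises these to about 10% and 23%, and the reversed arm pattern would overstate the effect instead. All of this rests on the assumed SD, correlation, dropout rule and carried-over loss rate; Visit 6 was not simulated. Recovery with earlier visits was shown for dropout driven by an observed score. Dropout driven by the unseen outcome would not be fully corrected.

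**What to change.** - **SAP 13.2:** analyse MADRS and CGI-S (Visits 4–7) and GAF (Visits 5–7) with a mixed model over all post-randomisation visits, adjusted for the Visit 3 value and the stratifying variable, with visit, arm and their interaction. Report the Visit 6 and Visit 7 contrasts. State the missing-data assumption and the covariance structure. The recovery in step 4 came from an estimator that let each earlier visit carry its own weight, so a single random intercept may recover less.
- **HDRS at Visit 7:** take the contrast from the mixed model already planned.
- **Synopsis, protocol 11.8 and SAP 10.2:** make them agree on which outcomes are weighted and on what handles missing data in the others.
- **Optional sensitivity analysis:** for remission and response, impute the missing scale score from earlier visits and arm before applying the cut-off.

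The cost is SAP wording and a few lines of code, plus a matching correction to the protocol synopsis. No new data are needed, and the sample size and primary analysis do not change. The downside is more model assumptions for exploratory outcomes.
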